10.1.1. Intensity of Adverse Events

Adverse events must be graded for intensity. An intensity category of mild, moderate, or severe, as defined in Table 6, must be entered on the AE eCRF. It should be noted that the term “severe” used to grade intensity is not synonymous with the term “serious.”

Table 6: Intensity of Adverse Events

Grade	Intensity
Mild	An AE that is usually transient and may require only minimal treatment or therapeutic intervention. The event does not generally interfere with usual activities of daily living.
Moderate	An AE that is usually alleviated with additional specific therapeutic intervention. The event interferes with usual activities of daily living, causing discomfort but poses no significant or permanent risk of harm to the research subject.
Severe	An AE that interrupts usual activities of daily living, or significantly affects clinical status, or may require intensive therapeutic intervention.

AE=adverse event.

10.1.2. Relationship to Study Treatment

The investigator will document his/her opinion of the relationship of the AE to treatment with study treatment using the criteria outlined in Table 7. An AE is deemed associated with the use of the study treatment “if there is a reasonable possibility that the treatment caused the AE” (otherwise referred to as a suspected adverse reaction). Reasonable possibility means there is evidence to suggest a causal relationship between the study treatment and the AE (Title 21 Code of Federal Regulations [CFR] 312.32 [a]).

Table 7: Relationship of Adverse Events to Study Treatment

Relationship	Description
Definite	The AE follows a reasonable temporal sequence from administration of the study treatment, abates upon discontinuation of the study treatment, follows a known or hypothesized cause-effect relationship, and (if appropriate) reappears when the study treatment is reintroduced.
Possible	The AE follows a reasonable temporal sequence from administration of the study treatment and cannot be reasonably explained by the known characteristics of the subject’s clinical state, environmental, or toxic factors, or other modes of therapy administered to the subject. There should be some evidence to support a causal relationship between the study treatment and the AE.

Relationship	Description
Unlikely	The temporal sequence between the AE and the study treatment is such that the study treatment is not likely to have any reasonable association with the AE or other plausible explanations exist for the AE (eg, disease, other drugs).
Not related	The AE does not follow a reasonable temporal sequence from administration of the study treatment, may not abate upon discontinuation of the study treatment, does not follow a known or hypothesized cause-effect relationship, and (if applicable) may not reappear when the treatment is reintroduced, furthermore, there may exist a clear alternative medical explanation (eg, underlying disease state) or association with study procedure or study conduct.

AE=adverse event.

10.2. Recording Adverse Events

For enrolled subjects, each AE will be listed as a separate entry on an AE eCRF. Screen failure subjects will have AE information noted only in the source document. The investigator (or designee) will provide information on dates of onset and resolution, intensity, seriousness, frequency, action(s) taken, changes in study treatment usage, relationship to study treatment, and outcome.

10.3. Poststudy Follow-Up of Adverse Events

All AEs, including clinically significant changes in ECGs, physical examination findings, or isolated clinically significant laboratory findings must be followed until the event resolves, the condition stabilizes, the event is otherwise explained, or the subject is lost to follow-up.

Adverse events ongoing at the final visit or at ET will be followed for as long as necessary to adequately evaluate the subject's safety or until the event stabilizes, resolves, or the subject is lost to follow-up. The investigator is responsible for ensuring that follow-up includes any supplemental investigations as may be indicated to elucidate the nature and/or causality of the AE. This may include additional laboratory tests or investigations, histopathological examinations, or consultation with other health care professionals, as is practical.

10.4. Serious Adverse Events

All SAEs will be recorded from the time the subject has signed the ICF (for subjects who do not enroll directly from Study NBI-827104-CSWS2010) or Day 1 (for subjects who enroll directly) until the final study visit. Investigators are not obligated to actively seek SAEs after a subject has withdrawn from or completed the study. However, if the investigator learns of any SAE, including a death, at any time after a subject has been withdrawn from or has completed the study, and the investigator considers the event to be reasonably related to the study intervention or study participation, the investigator must promptly notify the Sponsor as described in [Section 10.4.3](#).

10.4.1. Definition of a Serious Adverse Event

An SAE is any AE that results in any of the following outcome:

- Death.
- A life-threatening AE. Life-threatening means that the subject was, in the view of the investigator or Sponsor, at immediate risk of death from the reaction as it occurred. It does not mean that hypothetically the event might have caused death if it occurred in a more serious form.
- Inpatient hospitalization or prolongation of existing hospitalization. Hospitalization for elective treatment or a preexisting condition that did not worsen during the clinical investigation is not considered an AE. Hospitalization or nursing home admission for the purpose of caregiver respite is not considered an AE. Complications that occur during hospitalization are AEs, and if a complication prolongs hospitalization, the event is considered serious. Treatment in a hospital emergency room is not a hospitalization.
- A persistent or significant incapacity or substantial disruption of a person's ability to conduct normal life functions.
- A congenital anomaly/birth defect.
- Important medical events that may not result in death, be life-threatening, or require hospitalization. These events may be considered serious when, based on appropriate medical judgment, they may jeopardize the health of the subject and may require medical or surgical intervention to prevent one of the outcomes listed. Any other event thought by the investigator to be serious should also be reported, following the reporting requirements detailed in this section. Examples of such medical events include allergic bronchospasm requiring intensive treatment in an emergency room or at home, blood dyscrasias, convulsions that do not result in inpatient hospitalization, or the development of drug dependency or drug abuse.

10.4.2. Managing Serious Adverse Events

Subjects experiencing an SAE or an emergency situation will be examined by a physician as soon as possible. The physician in attendance will do whatever is medically needed for the safety and well-being of the subject. The subject will remain under observation as long as medically indicated. Appropriate laboratory studies will be conducted until all parameters return to normal or are otherwise explained or stable. The subject will be followed until the SAE resolves or until the subject is medically stabilized.

10.4.3. Reporting Serious Adverse Events and Other Immediately Reportable Events

SAEs and pregnancies must be reported within 24 hours of first knowledge of the event by study personnel to Neurocrine Biosciences, Inc. (NBI) Drug Safety and Pharmacovigilance (DSPV). Reports of SAEs and pregnancies must be followed by a fax or email of the SAE or Pregnancy Form (Table 8). It is important that the investigator provides his or her assessment of relationship to study treatment at the time of the initial SAE report. The investigator (or designee) will also

notify the IRB/IEC, if necessary) of the SAE and the outcome of the SAE, as required by the IRB/IEC.

Additionally, the following category of medical events that could occur during participation in a clinical study must be reported within 24 hours to the study Medical Monitor: events of suicidal behavior or suicidal ideation type 4 (active suicidal ideation with some intent to act, without specific plan) or type 5 (active suicidal ideation with specific plan and intent) based on the C-SSRS or clinical impression. Contact information for the study Medical Monitor will be provided to the study sites.

Table 8: Contact Information for Drug Safety and Pharmacovigilance

Facsimile	
Email	

10.4.4. Expedited Safety Reports

The Sponsor or its representatives will submit an Expedited Safety Report for any suspected adverse reaction ([Section 10.1.2](#)) that is considered both serious and unexpected within 15 calendar days and for any unexpected fatal or life-threatening experience within 7 calendar days to the applicable regulatory authority(ies); or according to country-specific regulations.

The Sponsor or its representatives will send copies of each safety report submitted to regulatory authorities to the investigators. The safety report must be submitted to the appropriate IRB/IEC as soon as possible. Documentation of the submission to the IRB/IEC and receipt by the IRB/IEC (if applicable) must be retained for each safety report.

10.5. Urgent Safety Measures

If an event occurs that is related to the conduct of the study or the development of the study treatment, and this new event is likely to affect the safety of subjects, the Sponsor and the investigator will take appropriate urgent safety measures to protect subjects against any immediate hazard. The Sponsor will work with the investigator to ensure the IRB/IEC and local regulatory authority are notified within 3 days or in accordance with applicable local laws and regulations.

10.6. Pregnancy

Pregnancy is neither an AE nor an SAE unless the criteria for an SAE are met. However, all pregnancies in subjects who received NBI-827104 will be followed to assess for pregnancy outcome. Subjects of childbearing potential must be counseled at all visits to continue using contraception ([inclusion criterion #3](#), Section 5.1) until 90 days after the last dose of study treatment. If a female subject believes she is pregnant at any time between signing the ICF and the last study visit, she should return to the study center within 24 hours and undergo a serum pregnancy test. Female subjects confirmed to be pregnant will be discontinued from the study treatment and withdrawn from the study.

All confirmed pregnancies in female subjects or in female partners of male subjects who received study treatment must be immediately reported to NBI (contact information is provided in [Section 10.4.3](#)), followed by fax or email of the pregnancy form to NBI DSPV. A first

trimester ultrasound may be requested for all confirmed pregnancies. Pregnancies in subjects who received NBI-827104 will be followed until resolution (ie, termination [voluntary or spontaneous] or birth).

Male subjects with female partners who become pregnant during the study must notify the study center as soon as possible. The study center will ask to follow the subject's partner's pregnancy.

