7.2. Dietary and Other Restrictions

VNS settings and/or a ketogenic diet must be stable from [REDACTED] prior to Day 1 (for subjects who do not enroll directly from or participate in Study NBI-827104-CSWS2010) or Day 1 (for subjects who enroll directly from Study NBI-827104-CSWS2010) and through the first [REDACTED] of study treatment (adjustments are not allowed). After the first [REDACTED] of study treatment and for the remainder of the study, a ketogenic diet may be started or adjusted and a VNS may be implanted or adjusted.

[REDACTED] are prohibited from within [REDACTED] prior to screening (for subjects who do not enroll directly from or participate in Study NBI-827104-CSWS2010) or Day 1 (for subjects who enroll directly from Study NBI-827104-CSWS2010) and until the end of the subject's participation in the study.

██████████ is prohibited from within ██████████ prior to screening (for subjects who do not enroll directly from or participate in Study NBI-827104-CSWS2010) or Day 1 (for subjects who enroll directly from Study NBI-827104-CSWS2010) and until the end of the subject's participation in the study.

Male subjects of childbearing potential must agree to refrain from donating sperm during the study and for 90 days after the last dose of the study treatment.

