8.2. Withdrawal from Study

If a subject prematurely withdraws from the study, the investigator will record the reason for withdrawal on the relevant eCRF. All subjects who withdraw from the study prematurely will be asked to have all ET assessments performed as soon as feasible and, unless consent has been withdrawn, will be asked to have a Safety Follow-Up phone call and visit approximately 1 week and 4 weeks after the last dose of study treatment, respectively. If a subject's last dose of study treatment was >1 week before the ET Visit, no additional phone call is needed; if a subject's last dose of study treatment was >4 weeks before the ET Visit, no additional visit is needed.

Reasons for withdrawal from the study include, but are not limited to:

- Withdrawal by the subject or parent(s)/legal guardian(s)
- AE
- Death

- Lost to follow-up
- Site terminated by Sponsor
- Study terminated by Sponsor
- Protocol deviation
- Investigator decision
- Sponsor decision

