Pregnancy test: Pregnancy tests will be performed throughout the study for female subjects of childbearing potential. A serum β -hCG pregnancy test will be performed at screening for subjects who do not enroll directly. A urine pregnancy test (using a urine pregnancy kit provided by the central laboratory) will be performed at the postscreening timepoints indicated in the Schedules of Assessments (Table 10 and Table 11). Female subjects who become of childbearing potential during the study will be required to undergo pregnancy testing at the timepoints indicated in the Schedule of Assessments (Table 10). Serum pregnancy tests should be performed if urine cannot be collected. Any positive urine pregnancy test should be confirmed by a serum pregnancy test.

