9.4.4.2. End of Study [REDACTED]

The Safety Follow-Up Visit is the final study visit.

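### Protocol 10.6 sets precautions to 90 days after the last dose, but its instructions to tell the site of a pregnancy stop at the last visit, about 4 weeks after that dose.

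*Protocol*

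**What the plan says.** **Precautions.** Protocol 10.6 requires contraception counselling at every visit, with contraception continuing "until 90 days after the last dose of study treatment". Protocol 7.2 asks male subjects to "refrain from donating sperm during the study and for 90 days after the last dose of the study treatment".

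**What brings a pregnancy to the site's attention.** Both instructions are in 10.6. The female subject's opens "If a female subject believes she is pregnant at any time between signing the ICF and the last study visit" and sends her back to the center for a serum test. The male subject's reads "Male subjects with female partners who become pregnant during the study must notify the study center as soon as possible".

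**When the last visit is.** Section 9.4.4.2 says "The Safety Follow-Up Visit is the final study visit". Section 8.2, on early withdrawal, places the follow-up phone call and "visit approximately 1 week and 4 weeks after the last dose of study treatment, respectively". For completers the timing is redacted (4.1.6, 9.4.4).

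**What the site must do once it knows.** Section 10.6 requires confirmed pregnancies in treated female subjects, and in partners of treated male subjects, to be reported to the sponsor, and pregnancies in treated subjects to be followed to outcome. Section 10.4.3 sets a 24-hour clock that starts when study staff first learn of the event. None of these duties has an end date.

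**Test schedule.** Section 9.3.7 cites Tables 10 and 11 for urine pregnancy tests in general, but only Table 10 for girls who become of childbearing potential during the study.

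**The concern.** The protocol regards the 90 days after the last dose as a period that still calls for precautions, and it intends to follow pregnancies in treated subjects. For most of that period, no text that can be read tells a subject, a family or a male subject to let the site know. An open-ended duty that starts when the site learns of a pregnancy works only if someone tells the site. After the final visit, that is left to chance.

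The situation can arise. Rollover subjects were 4 to 12 years old on entering the parent study, de novo subjects are 4 to 12 on entering this one, and treatment may last up to 234 weeks. Section 9.3.7 itself expects some girls to reach childbearing potential during the study. At stake is outcome information on a few possible pregnancies conceived shortly after treatment with an investigational drug. The primary endpoint, serious TEAEs, and its analysis are not affected.

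**Working it through.** **Inputs**
- Precaution window: 90 days after the last dose (Protocol 7.2 and 10.6).
- Last visit: about 4 weeks, taken as 28 days, after the last dose (Protocol 8.2, early withdrawal only).
- Maximum participation about 242 weeks and maximum treatment 234 weeks (Protocol 1). Treatment includes the taper (Protocol 4.1).
- Maximum screening: 28 days, or 4 weeks (SAP 3).

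**Step 1: does 4 weeks also fit completers?**
Follow-up = participation − treatment − screening = 242 − 234 − 4 = 4 weeks. This agrees with 8.2, so the same timing is a reasonable inference for completers.

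**Step 2: size of the gap**
- Visit at day 28: 90 − 28 = 62 days; 62/90 = 68.9%.
- Visit assumed at day 21: 90 − 21 = 69 days; 69/90 = 76.7%.
- Visit assumed at day 35: 90 − 35 = 55 days; 55/90 = 61.1%.
- Outer bound, counting all 242 − 234 = 8 weeks as follow-up (day 56): 90 − 56 = 34 days; 34/90 = 37.8%. The gap shrinks but does not close.

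**Step 3: the same gap against the whole period at risk**
Maximum treatment plus 90 days = 234 × 7 + 90 = 1638 + 90 = 1728 days; 62/1728 = 3.6%.

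**Step 4: age at the end of treatment**
234/52.2 ≈ 4.5 years. A subject who is 12 (up to just under 13) on Day 1 would be about 16.5 to 17.5 after maximum treatment.

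**Step 5: can the male instruction be read to cover the 90 days?**
Section 7.2 names the study and the 90 days after the last dose as two separate stretches of time. On the protocol's own usage, the phrase during the study in 10.6 does not by itself reach day 90.

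**The case against.** **The reporting duty does not end.** A reader might infer from the narrow windows that the duty to report stops at the last visit and that a later pregnancy would be neither reported nor followed. The documents do not support that. The duty in 10.6 depends on having received treatment, not on still being in the study, and the clock in 10.4.3 has no cut-off. A pregnancy that the site hears of on day 60 is reportable. This stands, and it limits the point to how the site comes to hear.

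**The female subject's sentence is on-study management.** It leads to a serum test and, if positive, to stopping treatment. Stretching it to day 90 would call former subjects back for a visit and a test. This also stands, and the sentence should be left alone.

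**Relevant text cannot be seen.** Section 5, with the contraception criterion that 10.6 cites, is redacted. The consent form and both schedules are not available. Counselling at every visit on its terms includes the final one, and a request to notify may be given there. This is a real limit on what can be claimed. It does not reconcile the windows that 10.6 states.

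**The gap is small.** Over the whole period at risk it is 3.6%, in about 24 children, with no count of those of childbearing potential. That is true and keeps the point modest. The 69% describes only the post-dose period.

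**Table 10.** A reader might infer that girls who escalate to DL 4, and so move to Table 11, go untested. Section 9.3.7 already applies both tables to female subjects of childbearing potential, so the single citation is an editorial slip.

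**Conclusion.** The stated notification windows in 10.6 are narrower than the protocol's own precaution window. About 62 of the 90 post-dose days (69%; 61% to 77% for a visit between day 35 and day 21) carry no visible instruction for a subject, a family or a male subject to notify the site. The duty to report and follow confirmed pregnancies continues through those days but has no trigger to set it off.

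This rests on the 4-week timing, which is explicit for early withdrawal and inferred for completers, and on the readable text alone. The length of the 90-day period is a clinical rule and is not judged here. The point is a cheap improvement to safety follow-up. It does not touch sample size, the primary endpoint or any planned analysis.

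**What to change.** 1. In Protocol 10.6, add a sentence asking female subjects (or their families) and male subjects to notify the site of any pregnancy, including a partner's, that occurs up to the end of the protocol's existing 90-day post-dose period. Bring the male-subject sentence into line with it.
2. Have the site give this instruction at the Safety Follow-Up Visit, and check that Section 5 and the consent form say the same.
3. Leave the on-study sentence on returning for a serum test unchanged. The existing duties in 10.4.3 and 10.6 then apply to whatever is notified.
4. Editorial: in 9.3.7, cite Table 11 as well as Table 10 for girls who become of childbearing potential.

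The cost is a sentence or two of protocol text, one added citation and a line in the end-of-study instructions, with no added visit or test. The downside is a few possible notifications after the final visit, which the safety database can take.

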11. STATISTICAL METHODS

This section represents a brief description of the planned primary analysis of the primary and secondary endpoints. A comprehensive and detailed statistical analysis plan (SAP) will be generated and finalized prior to study database lock. The SAP will provide additional details regarding the methods of analysis summarized in this protocol, describe analysis methods for other endpoints, describe analyses to characterize the study conduct and population, and may describe sensitivity and supplementary analyses for selected endpoints.

11.1. Statistical Hypothesis

There will be no formal hypothesis testing of the primary endpoint.

11.2. Sample Size Determination

A total sample size of up to approximately 24 male and female subjects is based on the sample size of Study NBI-827104-CSWS2010. At least 12 subjects are targeted to complete Week 12 at the highest DL evaluated in the study.

11.3. Analysis Sets

Statistical analysis sets used in this study are defined in Table 9. Additional analysis sets may be specified in the SAP.

Table 9: Analysis Sets

Population	Description
Full analysis set	The full analysis set will include all enrolled subjects who receive at least 1 dose of study treatment and have any efficacy data collected after the Day 1 Visit.
Safety analysis set	The safety analysis set will include all enrolled subjects who take at least 1 dose of study treatment.
[REDACTED]	[REDACTED]

11.4. Endpoints

For the endpoints below, [REDACTED]
[REDACTED]. The Treatment Period includes a [REDACTED] Dose Titration Period. Additional endpoints may be described in the SAP.

11.5. Statistical Analyses

Descriptive statistical methods will be used to summarize the data from this study. Descriptive statistics typically include the number of subjects (n), mean, standard deviation or standard error, median, first and third quartile, minimum, maximum, and CIs for continuous variables; and refers to the number and percentage of subjects for categorical variables.

Unless otherwise specified, the assessments collected at the Day 1 Visit will be used as baseline.

[REDACTED] Additional definitions of baseline may be specified in the SAP.

11.5.1. [REDACTED]

